1. STUDY SUMMARY

TITLE

The Sono-VE Study: Assessing the acceptability and feasibility of transperineal ultrasound and developing an ultrasound based predictive model for labour outcome.

DESIGN

This is a prospective observational study of transperineal ultrasound between 24-42 weeks gestation and a prospective longitudinal observational study in all term (37-42 weeks) labouring women.

AIMS

This study aims to **firstly** assess the effectiveness and acceptability of transperineal ultrasound in women presenting between 24 and 42 weeks gestation in comparison with digital vaginal examination (VE). **Secondly**, in all term (37-42 weeks) labouring women, we aim to create an ultrasound based labour record, “a sonopartogram” and from this develop a predictive model for the outcome of labour.

NULL HYPOTHESIS

That transperineal ultrasound

- 1) is not an acceptable or feasible technique in comparison with digital VE between 24 and 42 weeks gestation
- 2) cannot be used to predict labour outcome in term (37-42 weeks) labouring women.

OUTCOME MEASURES

Primary measures:

1. Assessing feasibility of ultrasound by comparison with digital vaginal examinations:

- *Digital vaginal examination:* cervical dilatation, head station, caput, moulding, head position
- *Ultrasound:*
 - *Transabdominal Ultrasound:* Fetal head position
 - *Transperineal Ultrasound:* Cervical dilatation, head-perineum distance, caput and moulding

2. Acceptability of Transperineal Ultrasound to patients

3. Dataset for predictive model of outcome of labour of Caesarean section due to failure to progress and/or fetal distress

- Time to delivery
- Mode of delivery
- Primary indication for delivery
 - failure to progress
 - suspected fetal compromise

Secondary measures:

1. Neonatal outcome

- Gender
- Birth-weight
- Apgar Scores at 1 and 5 minutes
- Cord Gases
 - Fetal acidosis defined as arterial pH <7.10 and base excess >12.0mmol/l
- Neonatal unit admission within 24 hours
- Neonatal morbidity

ELIGIBILITY

All pregnant women booked at Imperial College Healthcare NHS Trust between the ages of 18 and 44 able to give consent

DURATION

The duration of the study is 3 years.

Keywords

Preterm, PPROM, labour, intrapartum, vaginismus, placenta praevia, transperineal ultrasound.

2. Introduction

Recently, research has shown that fetal Doppler examination demonstrating cerebral distribution (low cerebro-umbilical [C/U: MCA/PI] ratio) in advance of labour may be able to predict emergency Caesarean sections¹⁶. This challenges previously thought to be protective effect of cerebral redistribution¹⁷ to perfuse the brain secondary to hypoxic insult and may help us to develop a model for Caesarean sections for presumed fetal distress.

2.2 Study Rationale and Hypothesis

Several studies have assessed the accuracy of transabdominal ultrasound in comparison with digital VE in determining fetal head position¹⁸⁻²¹. These have concluded that digital VE fails to identify the correct fetal head position in the majority of cases, especially at cervical dilatation $\leq 3-4\text{cm}$. Although transperineal ultrasound has been used pre-labour to predict the likelihood of PPROM patients going into labour²², its feasibility has not yet been assessed in the investigation and management of women either presenting with or established in labour. Initial studies have assessed head descent¹² and rotation²³ and angle of progression in labour^{13,24} to assess the second stage of labour to predict the likelihood of spontaneous vaginal delivery, instrumental delivery or Caesarean section. However, there have not been any studies directly assessing the feasibility of transperineal ultrasound scans.

We hypothesise that transperineal ultrasound will be a feasible and acceptable technique in comparison with digital vaginal examinations for 24-42 weeks gestation.

Using the data gathered in term patients, we will develop a model to predict pregnancy outcomes. This may aid in delivery of care to pregnant women by providing a real-time online calculation tool for the likelihood of vaginal delivery and length of labour based on repeat ultrasound measurements. This will allow a more

accurate prediction of the mode of delivery and reduce the number of vaginal examinations. This will improve the information available to women and their birth partners about the progress of their labour.

We anticipate improvements to women's health with additional information allowing better decision-making during labour enhancing the accurate recording of labour to a recordable skill. Universally, it may reduce the frequency of intrusive internal examinations and associated infection and will also be potentially useful in allowing the assessment of women in whom digital VE is traumatic or contra-indicated.

Overall, it may create a paradigm shift on delivery units in an area where the standard assessments have not changed in over one hundred years allowing better provision of resources.

3. Study Objectives

Primary objectives:

1. Feasibility of transperineal ultrasound scanning
2. Acceptability of transperineal ultrasound scanning
3. Creation of a "Sonopartogram" (Figure 3); an ultrasound based labour record
4. Prediction model of time to delivery and mode of delivery at term
 - Caesarean section due to failure to progress and/or fetal distress

Secondary objectives:

1. Creation of a digital representation of the progress of labour (Figure 4).

4. Methodology and Design

4.1 Study Centre

The study will be conducted at Queen Charlotte's and Chelsea Hospital (Primary centre of the study) and St Marys Hospital at Imperial College Healthcare NHS Trust.

There will be:

- A named individual (Clinical Research Fellow) in the relevant Study centre responsible for co-ordinating the project locally, and reporting directly to the chief investigators known as the project manager
- Regular inspection by the project manager, under the supervision of the chief investigator, will be carried out ensuring that both the service (literature, communication, documentation, supervision and logistics) and facilities (Ultrasound, equipment and space) are of high standards.
- All those who contribute are experienced in ultrasound. Suitably trained doctors and midwives (including research midwives) may contribute data to study where this is agreed in advance with the Principal Investigator.
- This study will form part of a PhD thesis and/or other higher degrees.

4.2 Design

This is a prospective observational study of transperineal ultrasound between 24-42 weeks gestation and a prospective longitudinal observational study in all term (37-42 weeks) labouring women.

4.3 Duration

The duration of the study is 3 years.

4.4 Inclusion Criteria

- Gestation 24-42 completed weeks at study entry
- Aged 18-44
- Cephalic
- Singleton pregnancies
- Nulliparous
- Multiparous (excluded for the term predictive model group)
- Multiple pregnancies (excluded for the term predictive model group)
- Established (Active) phase of labour (included for the term predictive model group)

- Clinician opinion that patient is in the established phase of labour according to the current NICE guidelines²⁵

4.5 Exclusion Criteria

- Younger than 18 years.
- Imminent iatrogenic intention to deliver
- Life threatening maternal or fetal compromise needing immediate medical attention and/or delivery
- Women who in the opinion of the researcher by virtue of language or learning impairment would be unable to give fully informed consent to the study.
- Miscarriage
- Intra-uterine death
- Previous cervical surgery eg. cone biopsy, cervical cerclage. Note- Single LLETZ is not excluded.
- Non-cephalic presentations
- Multiple pregnancies (for the term predictive model group)
- Multiparous patients (for the term predictive model group)
- Not in established labour (for the term predictive model group)

4.6 Withdrawal Criteria

Patients may be withdrawn from the study at any stage and all data captured in relation to their participation may be destroyed if they so request.

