4.9 Method of study

For each of the **two individual studies**, a **separate** information leaflet detailing the purpose will be provided to all potential recruits (see supporting documents and flow chart- **figure 7**). If a patient is willing to participate, written consent will be obtained.

The patients will then take part in a researcher led Reproductive Health interview which includes routine demographic data and information regarding previous obstetric, medical and gynaecological history, as well as questions regarding psycho-sexual health history. Where possible, the demographic and sensitive information relating to participants such as the ethnicity, obstetric and mental health history will be obtained by the researcher from the participants notes. All information will be entered into a secure study database. Patients will be identified by study number only.

During the ultrasound examination, women will be in the supine position with flexed hips and knees and the bladder empty as previously described. Healthcare professionals will be blinded to the ultrasound findings and these findings will also not be disclosed to the parents. Another doctor or midwife will perform all the ultrasound examinations.

Fetal position will be assessed with a transabdominal scan and recorded with half hourly divisions⁷. Thereafter, the transducer will be placed transperineally at the level of the posterior fourchette in a transverse position (Figure 1), and cervical dilatation¹⁴ and head-perineum distance (HPD) measured as previously described²². Caput succedaneum will be measured in a sagittal transperineal scan^{9,15} (Figure 1). Moulding will be assessed as either present or not¹².

The healthcare professional will perform digital vaginal examination assessing cervical dilatation, fetal head descent and position. The descent will be categorised using the WHO classification of fetal head station with the ischial spines as reference point 0, -5cm at the pelvic inlet and +5cm at the pelvic outlet²⁷.

Acceptability and Feasibility:

In this group, patients will also be asked to complete two additional researcher-led questionnaires (modified from a previously validated questionnaire -see supporting documents). This will be in the form of a “pre-study” and a “post-study” questionnaire which will focus on the patient’s views regarding vaginal examinations and the transperineal scanning method to assess the acceptability of the technique.

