4.12 Patient Engagement

Patients were involved in the creation of the initial study¹⁵ through the Cambridge Maternity Services Liaison Committee, and their feedback from the participation helped shape this research proposal. We have received outline support for the project from the RCOG Intrapartum Care Clinical Study Group led by [name] in 2012 and lay representatives, though this latest iteration of the project design has not yet been submitted to the group. Patient views are important in designing this study to maximise recruitment and we have previously consulted the RCOG to invite lay members to steering committees of a similar previous study (Transvaginal Ultrasound Scanning – Hazard and Clinical Practice, awarded CCF Grant, 2012). We will arrange Parent Focus Group Meetings alongside their hospital Parent Craft classes so they do not have to devote extra time to this and explore how they feel this research should be conducted. As well as active recruitment, they will also be allowed to self-volunteer to take part in the study with leaflets in various clinical areas. The Imperial Trust website also fosters public interest by including

links to the Clinical Research Network Coordinating Centre, Women's Health Research Centre and to the ongoing various projects.

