6.3 Reporting procedures

All adverse events will be reported. Depending on the nature of the event the reporting procedures below will be followed. Any questions concerning adverse event reporting will be directed to the Chief Investigator in the first instance.

Non serious AEs

All such events, whether expected or not, will be recorded.

Serious AEs

An SAE form will be completed and faxed to the Chief Investigator within 24 hours. However, relapse and death and hospitalisations for elective treatment of a pre-existing condition do not need reporting as SAEs.

All SAEs will be reported to the Chief Investigator who will determine if the event was:

- **Related-** resulted from the administration of any of the research procedures; and
- **Unexpected-** an event that is not listed in the protocol as an expected occurrence
- **Unrelated-** an event that is not related to the study

Reports of related and unexpected SAEs will be submitted within 15 days of the Chief Investigator becoming aware of the event, using the NRES SAE form for non-IMP studies. The Chief Investigator will also notify the Sponsor of all SAEs.

Local investigators will report any SAEs as required by their Local Research Ethics Committee, Sponsor and/or Research & Development Office.

Contact details for reporting adverse events:

Chief Investigator:

[name] MD MRCOG

Consultant in Obstetrics and Feto-maternal Medicine

Centre for Fetal Care, Queen Charlotte's & Chelsea Hospital

[name]

E-mail: [contact]

[contact]

7. Study Population and Sample size

Recruitment will start upon approval of the study. The infrastructure, research fellow, ultrasound machines, and the database are already in place, which ensure that the study can start promptly upon approval, without affecting or compromising routine clinical service provision.

We aim to recruit minimum number in the groups according to the following calculations²⁹:

Primary outcome:

Acceptability

In studies thus far, acceptability of transperineal ultrasound (with no or minimal pain) varies from 68%³⁰ to 95%³¹ compared with 20% for vaginal examinations³⁰. Using the lowest percentage of acceptability at 68%, with an alpha of 0.05 and a power of 90%, the minimum sample size required is 42 patients. However, given that this area has been poorly researched before and the power calculation is purely indicative, we would expect to collect at least 100 questionnaires.

Feasibility

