7.1 Statistical and Data Analysis

In both groups, data will be collected prospectively and compared with vaginal examinations. In the second group, there will also be additional longitudinal measurements.

We will use a p value of <0.05 to indicate significance.

All measurements will be entered online at the time of examination to a secure database on the Imperial College Healthcare NHS Trust shared server where the patient will be identified by study number only. The database entry page will be accessible to investigators on their login, though they cannot interrogate data already entered. The data rules will follow closely to those performed through the recently completed multicentre European TRUFFLE study of fetal growth restriction where ultrasound measurements were captured at the time of examination³⁷.

For 24-42 weeks assessment of acceptability and feasibility:

Acceptability and preference will be tested using a questionnaire with Likert scale for discomfort, adapted from the W-DEQ Score³⁸

Feasibility of the ultrasound technique will be compared to digital VE for (a) total number of observations missing (head descent, position and cervical dilatation) during an admission on the delivery unit and (b) number of ultrasound examinations or digital VEs that could not be carried out for whatever reason where there was an intention to carry out a digital VE.

As a part of feasibility, *Reproducibility* between the *ultrasound and digital VE techniques* will be assessed both as a correlation (r) and agreement (using the Bland Altman method) between the ultrasound method and digital VE for head descent and cervical dilatation, and the Kappa statistic for head position.

Term predictive model:

The predictive value of intrapartum ultrasound parameters will be investigated using linear and logistic regression analyses. We will calculate the Receiver Operating Characteristic (ROC) curve with the Area Under the Curve (AUC) and associated positive and negative predictive values for delivery outcomes in the evaluation of transperineal ultrasound as a diagnostic tool.

8. Study supervision and Monitoring

Central and local supervision: the chief principal investigator at Imperial College London will be responsible for the protocol, quality control, interim analyses of the data, advice on progress and final analysis and reporting of the study. The Imperial Joint Research Compliance Office may audit the study as part of routine research governance.

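### Acceptability is scored only among consenting women; refusals, stopped scans and erased withdrawals do not reach it, so its absolute level is probably somewhat too high

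*Combined protocol and SAP*

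**What the plan says.** Acceptability to patients is listed as a primary measure in the study summary and in Section 5.1. Section 7.1 states how it is measured: "Acceptability and preference will be tested using a questionnaire with Likert scale for discomfort". Under Section 4.9 the questionnaires are given before and after the study procedures to women in the acceptability and feasibility group, all of whom have already agreed to take part: "If a patient is willing to participate, written consent will be obtained". Recruitment also uses posters and websites (Section 4.7), and Section 4.12 says of patients that "they will also be allowed to self-volunteer to take part in the study".

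Four other places bear on women who do not go through with the scan:

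- Section 9.2 respects refusal to take part without reasons. No log of refusals is described there or elsewhere in the text.
- Section 4.6 provides that, when a woman withdraws, "all data captured in relation to their participation may be destroyed if they so request". It does not say that the fact of withdrawal is kept as a count.
- Section 7.1, feasibility item (b), counts ultrasound or digital examinations that were not done, whatever the cause, when a digital examination was intended.
- Section 4.9 has a note made when a woman declines digital examination for psychological reasons. There is no matching rule for a woman who declines the scan.

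For planning, Section 7 says that "acceptability of transperineal ultrasound (with no or minimal pain) varies from 68" per cent to 95%, "compared with 20% for vaginal examinations", and that "with an alpha of 0.05 and a power of 90%, the minimum sample size required is 42 patients". It adds that "we would expect to collect at least 100 questionnaires".

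**The concern.** Declining the scan, or stopping it because of discomfort, is direct evidence about acceptability. The plan measures acceptability after that selection has taken place. A woman who reads the leaflet and says no is not counted at all in the visible text. An enrolled woman who refuses or stops a scan may appear under feasibility, mixed with scans missed for practical reasons, and nothing carries her into the acceptability result. A woman who withdraws and asks for her data to be destroyed can leave nothing behind, not even an anonymous tally mark.

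These omissions probably act in the same direction, in favour of the scan. This matters because Sections 2.1 and 2.2 put the scan forward for women who find digital examination traumatic, and some of them may not want a perineal probe either. With no uptake figure, a reader of the results could not tell whether a high questionnaire score describes women offered the scan or only those content to have it. Refusals not logged at the time cannot be recovered later.

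**Working it through.** **Inputs from the plan (Section 7).** Planning acceptability of the scan is 68%, with 95% as the upper published value. Vaginal examination is 20%. Alpha is 0.05 (sidedness not stated), power is 90%, the stated total is 42, and the practical target is at least 100 questionnaires.

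**Input not in the plan.** The share *r* of women approached who are missing from the result is assumed, and shown from 10% to 50%.

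**Step 1: the plan's own figure.** For two independent proportions, two-sided, without continuity correction, the mean proportion is (0.68 + 0.20)/2 = 0.44 and

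n per group = [1.960 × √(2 × 0.44 × 0.56) + 1.282 × √(0.68 × 0.32 + 0.20 × 0.80)]² / (0.68 − 0.20)²

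= [1.376 + 0.788]² / 0.2304 ≈ 20.3, rounded up to 21.

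The total is 2 × 21 = 42, which reproduces the stated number. The calculation has no term for women who decline or withdraw.

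**Step 2: worst case for decliners.** If every missing woman is counted as finding the scan unacceptable, the share among women approached is observed × (1 − r).

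| r (assumed) | observed 68% | observed 95% |
|---|---|---|
| 10% | 61.2% | 85.5% |
| 15% | 57.8% | 80.8% |
| 20% | 54.4% | 76.0% |
| 30% | 47.6% | 66.5% |
| 40% | 40.8% | 57.0% |
| 50% | 34.0% | 47.5% |

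**Step 3: break-even points.** An observed 68% falls to one half when r = 1 − 0.50/0.68 = 26.5%. It falls to the 20% planned for vaginal examination when r = 1 − 0.20/0.68 = 70.6%. This lowers only the scan's figure and leaves the 20% unchanged.

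**Step 4: erased withdrawals.** Suppose one woman who found the scan unacceptable is removed from a sample of 100. Then 68/100 becomes 68/99 = 68.7%, and 95/100 becomes 95/99 = 96.0%. Each such erasure adds about 0.7 to 1.0 percentage point.

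**Step 5: who is captured and where.**

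| Woman | Counted in | Reaches acceptability? |
|---|---|---|
| Declines the study | nothing in the visible text | no |
| Enrolled; refuses or stops the scan; digital examination intended | feasibility (b) if the scan was not carried out; no reason category | no rule links it |
| Enrolled; refuses the scan; assessed by speculum because digital examination is contraindicated | outside the wording of feasibility (b) | no rule links it |
| Withdraws and asks for destruction | no count required to survive | no |
| Withdraws without that request | her data may stay | no rule stated |
| Scanned, dislikes it, stays in | post-study questionnaire | yes |

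**The case against.** Several stronger readings are tempting, and the documents do not support them.

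- *All women who find the scan unacceptable disappear from the result.* They do not. A woman who is scanned, dislikes it and stays in reports this on the post-study questionnaire. The pre-study questionnaire should also hold the views of an enrolled woman who later refuses.
- *The plan counts no refusals.* Feasibility (b) covers an enrolled woman's scan that is not done for any cause, provided a digital examination was intended. What is missing is a reason, a link to acceptability, and any count of women who decline the study.
- *Withdrawal erases the woman.* Destruction is permissive and happens only if she asks. Section 4.11 also has recruitment noted in the hospital record. Section 4.6 protects participants' rights, and how far to alter it is partly an ethics question.
- *True acceptability is 48%.* That figure assumes both the refusal rate and that every decliner finds the scan unacceptable. Women may decline for other reasons, such as the interview with psycho-sexual questions, the extra questionnaires, or being approached on the labour ward. Decliners have also not had the scan, so they have no value on a measure of pain during it.
- *The comparison with vaginal examination is unsafe.* On the planning rates it would reverse only at about 71% missing, all unfavourable.

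It is also fair to say that any consented study is conditioned on consent. The leaflets, the questionnaires and the flowchart in Figure 7 are not available here and might provide for a log.

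These points narrow the concern and leave a gap. The visible text has no uptake denominator, no route from a refused or stopped scan to the acceptability result, and no count that must survive a destruction request.

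**Conclusion.** The point holds in a limited form. As written, the primary acceptability figure leaves out some of the women who find the scan unacceptable, and its absolute level is probably biased upward. The direction is a reasoned expectation; the documents do not prove it. The size cannot be determined, because they give no refusal or withdrawal rate. The worst-case fall from 68% to 58% at 15% refusal, or to 48% at 30%, is an outer bound for those assumed rates and should not be read as an estimate. The finding that the scan is better accepted than vaginal examination is not in doubt on this ground at any moderate rate of refusal. The question is how far the absolute figure can be applied to women offered the scan. The point is worth correcting because the data needed to judge it can be collected only during recruitment.

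**What to change.** Mainly in Section 7.1:

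1. Keep an anonymous tally of women approached, declining and withdrawing. Record a reason only if the woman volunteers one, which is consistent with Section 9.2. Report uptake beside the questionnaire result, without merging the two into one percentage.
2. Record the reason when an enrolled woman refuses or stops a scan, including where the comparison is with speculum examination.
3. Add a sensitivity analysis of acceptability in which discomfort-related refusals, stops and withdrawals among enrolled women count as not acceptable.

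In Section 4.6, add that when data are destroyed on request a non-identifying count of withdrawals is kept, and say so in the information leaflet. If the supporting documents or Figure 7 already provide a log, Section 7.1 need only refer to it and state how it will be used.

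The cost is one line per approach, a sentence in Section 4.6 and the leaflet, and a short addition to Section 7.1. For scale, 100 questionnaires at an assumed 30% refusal would mean logging about 100/0.70 = 143 approaches. The downside is slight clerical work and possibly a less favourable headline figure.
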